6.3.1. Donor Genotyping

We will ensure that subjects only receive a heart transplant from a confirmed Genotype 1 or 4 HCV-positive donor by testing the HCV genotype using the standard of care assay at the Hospital of the University of Pennsylvania.

To briefly outline this procedure, donor genotyping will be performed on specimens provided to the Molecular Pathology Laboratory by LABS and Gift-of-Life, the local organ procurement organization. These specimens will be taken from potential heart donors once Gift-of-Life has been notified of the potential donor and will be qualified for testing by Gift-of-Life. Per standard of care, LABS will analyze specimens for the presence of HCV via serological testing and qualitative nucleic acid testing. If a specimen is positive for both HCV tests, it will be couriered to the University of Pennsylvania via a Gift-of-Life courier, only if and after the donor's authorizing next-of-kin has given authorization for donation and research. The Molecular Pathology Laboratory (MPL) at the Hospital of the University of Pennsylvania (HUP) will then determine the HCV genotype(s) present in the specimen. Once resulted, a printed copy will be sent to Gift-of-Life and the study investigators, and will be kept in the locked research file by the study investigators.

The assay that will be used for HCV genotyping is a laboratory-developed assay that was validated by the HUP MPL under the guidance of [name] [name], PhD. The validation process entailed testing multiple past clinical samples with known HCV genotypes, as well as purchased HCV genotype controls, and assessing concordance between the results obtained and the expected results.⁹ This assay (the eSensor® HCVg Direct Test, GenMark Diagnostics) has also been validated by multiple external laboratories with the following results: Covance Central Laboratory Services (482 samples, 98.6% concordance), University of Minnesota (135 samples, 96.4% concordance), and the University of Washington (77 samples, 97.4%).¹⁰⁻¹² In the HUP MPL, overall, the assay was able to genotype all purchased controls correctly (n=15, HCV genotypes 1 through 6, concordance = 100%). It was also able to correctly genotype the vast majority of prior clinical samples (n=56 of 61, HCV genotypes 1 through 6, concordance = 92%). Resolution of discordant samples showed that the limitations of the assay, as determined by the validation, included decreased ability to genotype samples with: low viral loads, mixed genotype infections, or HCV genotype 4f infection. These limitations are felt to be minor as low viral load specimens are not expected from HCV-untreated organ donors, and mixed genotype / genotype 4f specimens are very rarely encountered in the United States. The validation samples were picked to better understand the limitations of the assay and so had a higher proportion of mixed infection samples (n=6) and rare genotype samples (e.g. Type 4f, n=1) than what is encountered clinically. A retrospective review by the MPL of HCV genotypes resulted at HUP over a 14-month period (July 2014 to October 2015) by the previous MPL HCV genotyping assay (Siemens VERSANT HCV Genotype 2.0) found a total of 6 mixed infections and one genotype 4f infection out of 1,551 samples tested (~0.4% and 0.06%, respectively).

6.3.2. Drug Resistance Testing

Participants with Genotype 1a and Genotype 1 with an unknown subtype will have baseline NS5A drug resistance assay testing checked at the start of treatment. The Hepatitis C Viral RNA Genotype 1 NS5a Drug Resistance test will be used to check for NS5A drug resistance. This test uses reverse transcription polymerase chain reaction (PCR) and DNA sequencing to detect mutations [resistance associated variants (RAVs)] in the NS5a inhibitors. It has not been cleared or approved by FDA but has been validated pursuant to the CLIA regulations. The test will be performed by a lab qualified by the Principal Investigator Team. It has an analytical sensitivity of >95% for viral loads ≥1800 IU/mL.¹³ Reported results include mutations and polymorphisms associated with NS5A inhibitor resistance (only if HCV genotype 1a, 1b, or 1 detected) as well as a patient specific interpretation:

- Resistance predicted: ≥1 mutation predicting NS5A inhibitor resistance detected

- Resistance not predicted: no mutations predicting NS5A inhibitor resistance detected

7 CHAPTER 4: TREATMENTS

7.1. Zepatier (grazoprevir and elbasvir)

Zepatier tablets will be provided by Merck as part of this investigator-initiated protocol funded by Merck. Open-label Zepatier (grazoprevir 100 mg and elbasvir 50 mg) will be administered once daily by mouth for 12 weeks. An exception to the 12 week course of treatment will be if patients have polymorphisms at positions M28, Q30, L31, and/or Y93 as determined by the Hepatitis C Viral RNA Genotype 1 NS5a Drug Resistance test. In this case, treatment with Zepatier will be extended to 16 weeks and renally-adjusted Ribavirin will be initiated at the clinician's discretion, and continued for the remainder of therapy (until the 16 week mark). Such a strategy will provide optimal treatment, without delaying therapy prior to receipt of results of NS5A drug resistant testing. Grazoprevir (GZR)/ elbasvir (EBR) is a fixed-dose combination tablet without ribavirin.

GZR is an HCV ns3/4a inhibitor while EBR is an HCV NS5A inhibitor. Both are direct-acting antivirals, which together form an effective therapy for HCV virus and reduce the likelihood and effects of long-term liver-related HCV complications. GZR/EBR exhibits broad in vitro activity against most HCV genotypes and in vitro activity against many clinically relevant resistance-associated variants (RAVs).

Zepatier (GZR/EBR) has been evaluated globally in multiple phase I, II, and III trials to treat HCV. Randomized, placebo-controlled trials have been completed and led to obtain FDA approval for Zepatier as a treatment for genotype 1 and 4 HCV. As of July 1, 2015, a diverse population of over 1000 HCV patients has been exposed to Zepatier either as a single agent or in combination with ribavirin or sofosbuvir in phase I/II/III studies. Zepatier has been generally well tolerated at doses of 50-100 mg GZR and 50 mg EBR orally once daily. It has been comparably effective across all subgroups it has been tested in, including non-cirrhotic and/or treatment-naïve subjects.

Headaches, fatigue, and nausea represent the most common adverse drug reactions with Zepatier. Other drug-related adverse events have included arthralgia, insomnia, diarrhea, dizziness, pyrexia, and asthenia. Drug-related serious adverse events are uncommon, but include allergic reactions, possible adverse interactions with other medications, or elevated liver enzymes. In past Zepatier trials, the majority of the adverse events were reversible. These adverse events are usually grade 1 or 2 mild or moderate events.

The dosage in our study (100/50 mg qd) is a commonly attainable dose in clinical practice. In the event dialysis is needed after transplant, Zepatier has shown to be safe for subjects with chronic kidney disease or who are on hemodialysis. Less than 1% of Zepatier is excreted renally. In Merck C-SURFER, a phase 1 randomized, controlled Zepatier trial, subjects with advanced heart disease tolerated the drug well for the required 12 weeks and had no need for dose adjustments.

Zepatier trials have demonstrated a 94-100% success rate achieving HCV RNA levels of <15 IU/ml after 12 weeks of treatment (SVR-12) among genotype 1 and 4 HCV patients.

As of January 2016, Zepatier was approved by the Food and Drug Administration. It has been extensively studied in multiple large clinical trials. This drug regimen was chosen as first-line therapy, rather than other approved agents (i.e., Sofosbuvir/Ledipasvir, trade name Harvoni), as Zepatier has been shown to be safe and efficacious in patient with significant renal dysfunction. As a result, if a subject's heart function has not fully recovered when treatment is initiated, the investigational agents can safely be administered, unlike other approved agents.

7.1.1. Administration of study medication

Merck & Co will manufacture, package, and label Zepatier drug. There will be one bottle per subject containing a 28-day supply (28 capsules) of 100/50 mg Zepatier tablets. Daily dose will be one tablet.

The Investigational Drug Services (IDS) pharmacy, directed by [name], will only be required to store and distribute the study drug. Sofosbuvir and Ribavirin will be purchased and sourced locally. Both of these medications will be purchased and stored by the IDS pharmacy at Penn. Ribavirin will be generic and the manufacturer will vary depending on monthly price fluctuations.

Zepatier will be picked up from the investigational drug services (IDS) pharmacy by the research staff at 28-day intervals. The study staff will deliver the medication to the subjects at their study visits (patients expected to be at home by the time that HCV therapy is initiated and patients will be given medication at their scheduled post-transplant/study visit). Treatment with the study drug will begin within 4 weeks post-transplant. If hepatitis C is not cured after a subject has received Zepatier, he or she will be treated with a second regimen that includes Zepatier plus Sovaldi (Sofosbuvir) and Ribavirin. Any patient (male or female) receiving ribavirin as part of the first- or second-line regimen will be required to use two methods of birth control while on Ribavirin therapy, with continuing two forms of birth control for up to 6 months after the last dose of the study drug.

If patients have baseline NS5A drug resistance assay testing that demonstrates polymorphisms at positions M28, Q30, L31, and/or Y93, treatment with Zepatier will be extended to 16 weeks, rather than 12 weeks, and renally-adjusted Ribavirin at the clinician's discretion will be initiated, and continued for the remainder of therapy (until the 16 week mark). Such a strategy will provide optimal treatment, without delaying therapy prior to receipt of results of NS5A drug resistant testing.

7.1.2. Drug logistics and accountability

Study medication bottles must be stored at controlled temperature of 20°C to 25°C (68°F to 77°F); excursions permitted between 15°C to 30°C (between 59°F to 86°F) in a locked, secure area. Study drug must be protected from moisture. The research staff or investigator will instruct the subject on the proper administration of Zepatier. Zepatier tablets should be taken once daily by mouth. The investigator, or a responsible party designated by the investigator, must maintain a careful record of the inventory and disposition of the investigational agent using the drug accountability form. If a subject loses the bottle of study medication, the research staff should contact [name], Pharmacist at the research pharmacy. A replacement bottle with the appropriate amount of study medication will be made available at the research pharmacy.

7.1.3. Destruction and return

At the conclusion of the study, remaining medication from the study patients (and left-over medication) will be destroyed at the clinical site, after approval is granted by the research pharmacy for the drug destruction plan. Destruction will be documented in the drug accountability form.

7.1.4. Zepatier Initial Treatment Failures

Study subjects with treatment failure, defined as virologic breakthrough (when an undetectable viral load while on treatment becomes detectable) or virologic relapse (undetectable viral load after completion of treatment that during the 12-week post-treatment follow-up period becomes detectable) will be provided open-label Zepatier + Sofosbuvir (Sovaldi) 400 mg + Ribavirin (generic), renally dosed based on creatinine clearance per the manufacturer guidelines. Any subjects who experience treatment failure will repeat the original study lab visit and visit protocol once they begin their secondary treatment with Zepatier, sofosbuvir, and ribavirin, similar to

subjects initiating HCV treatment following heart transplantation. Prior to initiating treatment with this regimen, patients will have serum NS5A resistance (RAV) testing.

8 CHAPTER 5: DATA COLLECTION

8.1. Study visits

Study visits are scheduled to occur following subjects' standard post-transplant follow-up visits. Since treating cardiologists do not always require stable post-transplant patients to attend these visits, subjects may be asked to come in solely for study visits. These visits will be encouraged, but not required unless the study drug is being dispensed that day. For all other study visits, a missed visit by a stable subject who has had necessary labs drawn will not be considered a protocol violation.

8.1.1. Informed consent

During the screening phase, potentially eligible, interested subjects will be invited to attend an informational session. The following procedures will be performed during the screening process:

- Sign and date the ICF and HIPAA authorization
- Review of inclusion/exclusion criteria
- Schedule for screening visit

After completing the informational session and signing the informed consent, the subject will be scheduled for a screening visit within 56 days if the subject meets inclusion/exclusion criteria thus far. The study staff will call the subject 1-2 days prior to the screening visit and send a reminder letter as well if the screening visit is not conducted within the 2 weeks following consent.

8.1.2. Screening

The following procedures and activities will be performed during the screening process, after the informed consent is signed:

- Review medical history
- Vital signs
- Physical exam
- Review current medications
- Labs/phlebotomy: hepatic function panel, HCV RNA, HBV DNA, and HIV antibody
 - HBV Core Antibody will be checked in patients during screening, if not checked previously.
- Serum chg. pregnancy test (for women of childbearing potential)
- Completion of health status questionnaire (RAND-36)
- Provide instructions on recording of new medications and dose changes

8.1.3. Post-Heart Transplant

8.1.3.1. Post-Heart Transplant Visits

Patients, after receiving a heart transplant are followed very closely by both the surgical and nephrology team. As apart of standard of care visits, the following procedures activities will be performed:

- Phlebotomy
- Vital signs
- Physical exam

The study staff will follow procedures and activities closely along with transplant team and this information (vital signs, physical exam, and phlebotomy results) will be collected as apart of data collection. In addition to these

standard of care procedures and activities, the study team will also perform specific research related activities at specific time points.

8.1.3.2. Post-Heart Transplant Research Phlebotomy

Research laboratory blood draws will take place along with standard of care blood draws outlined in Section 8.2.1. The study staff will call the research subject to coordinate research blood draws appropriately. In addition, study staff will assess for adverse events/side effects and obtain current medication data.

As outlined in Section 8.2.1, patients with a positive HBV Core Antibody, HBV-DNA levels will be checked every 6 weeks while on Zepatier and LFTs will be closely monitored. HBV therapy may be considered the transplant team as medically appropriate.

Additional laboratory testing will be done if the PIs feel it is necessary for patient safety.

8.1.3.3. Visit 1: Post-Heart Transplant (day 3 ± 1)

The study staff will meet the subject in their HUP hospital room, three days after their heart transplant.

Initiating treatment with Zepatier

Treatment with the study drug will begin when the patient has a detectable and quantifiable HCV RNA post-transplantation. All subjects will be provided with a 28-day supply of the study drug and instructed to begin treatment once HCV RNA is confirmed, which may occur any time between weeks 1-4. When the subject begins treatment for HCV with Zepatier, the staff will notify the subject's primary cardiologist and primary care physician.

As with any scientific protocol, safety will be considered before treating the patients. The treating physician will evaluate the patient's overall condition and make a judgment on whether initiating treatment is safe.

The following research procedures and activities will be performed:

- Assess for Adverse Events
- Obtain medication data
- Research Phlebotomy, including the NS5A drug resistance assay testing (See Section 8.2.1 for complete list)
- Dispense study drugs

Blood samples for immunologic t-cell assays will be processed and banked or shipped.

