8.1.3.7. Visits 5-7: Post-Heart Transplant (day 42±7, day 56±7, day 70±7)

Visit #5 should occur 6 weeks (42±7 days) after the subject's heart transplant and will coincide with the subject's regularly scheduled post-transplant follow-up visit. Visit #6 should occur 8 weeks (56±7 days) after the subject's heart transplant and will immediately follow the subject's regularly scheduled post-transplant follow-up visit. Visit #7 should occur 10 weeks (70±7 days) after the subject's heart transplant and will immediately follow the subject's regularly scheduled post-transplant follow-up visit.

For both visits, the staff will call the subject 1-2 days before the visit to remind subject of visit. During this phone call, the research staff will remind the subject where to go for the study visit, to take their routine and study medications as they usually would prior to the visits.

The following procedures and activities will be performed:

- Assess for Adverse Events
- Obtain medication data
- Research Phlebotomy (See Section 8.2.1 for complete list)
- Replenish study drug
- Pill count and drug diary assessed for adherence
- Schedule appointments for follow-up visits

The staff will replenish the subject's 28-day supply of the Zepatier study drug sometime during visits #5 & 6, depending on when the subject began treatment.

8.1.3.8. Visits 8 & 9: Post-Heart Transplant (day 87 + 7, day 115 + 14)

Visit #8 should occur 12 weeks (87 + 7 days) after the subject's heart transplant and will coincide with the subject's regularly scheduled post-transplant follow-up visit. Visit #9 should occur 16 weeks (115 + 14 days) after the subject's heart transplant and will immediately follow the subject's regularly scheduled post-transplant follow-up visit.

Midway between these study visits, subjects will be phoned in order to ensure drug adherence, if necessary

For both visits, the staff will call the subject 1-2 days before the visit to remind subject of visit. During this phone call, the research staff will remind the subject where to go for the study visit, to take their routine and study medications as they usually would prior to the visits.

The following procedures and activities will be performed:

- Assess for Adverse Events
- Obtain medication data
- Research Phlebotomy (See Section 8.2.1 for complete list)
 - Note: Timing for HCV RNA viral load, post treatment, should, as best possible, follow the important data collection points post treatment. These are as follows:

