 - Post-treatment: This should occur after the subject has completed treatment of the study drug.
 - SVR 4: This should occur ~4 weeks after the subject has completed treatment.
 - SVR 8: This should occur ~ 8 weeks after the subject has completed treatment.
 - SVR 12: This should occur ~12 weeks after the subject has completed treatment.
 - SVR 24: This should occur ~24 weeks after the subject has completed treatment.
- Health Status Questionnaire (RAND-36) (to assess changes in health status from pre- to post-transplant)
- Pill count and drug diary assessed for adherence
- Replenish study drug
 - Note: The staff will replenish the subject's supply of the Zepatier study drug between visits 7 & 8, if necessary. This is based on management of patients NS5A resistance variants, in any were are present . The staff will also remind the subject how to take the medication, for those subjects still on study medication.

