8.1.3.9. Visit 10 Post-Heart Transplant (day 171 ±7 days)

Visit #10 should occur 24 weeks (171 ±7 days) after the subject's heart transplant and will coincide with the subject's regularly scheduled post-transplant follow-up visit.

For this visit, the staff will call the subject 1-2 days before the visit. During this phone call, the research staff will remind the subject where to go for the study visit, to take their routine and study medications as they usually would prior to the visits.

The following procedures and activities must be performed:

- Assess for Adverse Events
- Research Phlebotomy (See Section 8.2.1 for complete list)
 - Note: Timing for HCV RNA viral load, post treatment, should, as best possible, follow the important data collection points post treatment. These are as follows:
 - Post-treatment: This should occur after the subject has completed treatment of the study drug.
 - SVR 4: This should occur ~4 weeks after the subject has completed treatment.
 - SVR 8: This should occur ~ 8 weeks after the subject has completed treatment.
 - SVR 12: This should occur ~12 weeks after the subject has completed treatment.
 - SVR 24: This should occur ~24 weeks after the subject has completed treatment.
- Health Status Questionnaire (RAND-36) (to assess changes in health status from pre- to post-transplant)

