8.2. Study schedule of procedures

8.2.1. Visits, lab testing, and other clinical testing

See next page for table.

Transplanting HCV Hearts into HCV Negative Heart Recipients

Protocol V.2.0. 06/09/2017

		Visit Schedule			Research Visit Activities				Research Labs						Standard of Care						
Week(s) post-KT	Day(s) post-KT	Visit	Study Visits	Lab-Only	Informed Consent	Assess Adverse Events	Current Medications	RAND-36 Health Status Questionnaire	HBV DNA HIV AB & LFTs	HBV Core Antibody	Urine Preg Test	Urine Protein/Creatinine Ratio	HCV RNA	Viral Kinetics (optional)♦	NS5A Resistance	Genotyping	Vitals & Physical Exam	Surveillance biopsy	CMP*	CBC	Tacrolimus
Screening					✓	✓	✓		✓	✓	✓		✓			✓			✓		
1 (Begin treatment)	3 ± 1 day	V1	✓			✓	✓		✓	✓			✓	✓	✓	✓	✓	✓	✓	✓	✓
1	7 ± 1 day			✓			✓						✓	✓					✓	✓	✓
2	10 ± 1 day	V2	✓			✓	✓						✓	✓				✓	✓	✓	✓
2	14 ± 1 day			✓			✓						✓	✓				¥	✓	✓	✓
3	21 ± 3 day	V3	✓			✓	✓						✓	✓				✓	✓	✓	✓
4	28 ± 3 day	V4	✓			✓	✓	✓					✓	✓	✓			✓	✓	✓	✓
6	42 ± 7 day	V5	✓			✓	✓			✓			✓	✓				✓	✓	✓	✓
8	56 ± 7 day	V6	✓			✓	✓						✓	✓				✓	✓	✓	✓
10	70 ± 7 day	V7	✓			✓	✓							✓				✓	✓	✓	✓
12	84 ± 7 day	V8	✓			✓	✓			✓			✓	✓	✓			✓	✓	✓	✓
13 (End treatment)†	91 ± 7 day			✓			✓							✓							
16 (SVR 4)†	112 ± 14 day	V9	✓ †			✓	✓	✓					✓	✓			✓ †	✓	✓	✓	✓
20 (SVR 8)	140 ± 7 day			✓									✓	✓				✓	✓	✓	✓
24 (SVR 12)	168 ± 14 day	V10	✓			✓		✓					✓	✓	✓			✓	✓	✓	✓
28†	196 ± 7 day			✓										✓				✓	✓	✓	✓
32	224 ± 7 day			✓										✓				✓	✓	✓	✓
36 (SVR 24)	252 ± 7 day			✓									✓	✓	✓			✓	✓	✓	✓
40	280 ± 14 day			✓										✓				✓	✓	✓	✓
52	365 ± 14 day	V11	✓			✓							✓	✓	✓			✓	✓	✓	✓

* CMP=comprehensive metabolic panel which includes basic metabolic panel and liver function tests

Viral Kinetics testing can be done anytime there is a standard of care blood draw. Only if HRV Core Antibodies are positive.

If patients require the 16 weeks of therapy, the last 4 weeks would be the same as weeks 9-12 of

◆ Viral Kinetics testing can be done anytime there is a standard of care blood draw.

■ Only if HBV Core Antibodies are positive

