8.2.2. Blood sampling volumes

Maximum Post-Transplant Blood Draw Totals								
Week Post-KT	CBC	CMP	Tacrolimus	HBV Core Antibody	HCV RNA	Viral Kinetics (optional)♦	NS5A Resistance	Blood Draw Total
1	4	4.5	4	4	6	6	2	28.5
1	4	4.5	4	0	6	6	0	24.5
2	4	4.5	4	0	6	6	0	24.5
2	4	4.5	4	0	6	6	0	24.5
3	4	4.5	4	0	6	6	0	24.5
4	4	4.5	4	0	6	6	0	18.5
6	4	4.5	4	4	6	6	0	24.5
8	4	4.5	4	0	6	6	0	24.5
10	4	4.5	4	0	0	6	0	18.5
12	4	4.5	4	4	6	6	0	28.5
16	4	4.5	4	0	6	6	0	24.5
20	4	4.5	4	0	6	6	0	24.5
24	4	4.5	4	0	6	6	0	24.5
28	4	4.5	4	0	0	6	0	18.5
36	4	4.5	4	0	6	6	0	24.5
40	4	4.5	4	0	0	6	0	18.5
52	4	4.5	4	0	6	6	0	24.5
Total	68	76.5	68	0	84	102	2	400.5

♦ There may be additional blood draws due to optional Viral Kinetics lab testing increasing the total sample volume.

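### The protocol conflicts on SVR-12 timing: the definition counts from the end of treatment, the scheduled draw counts from transplant, and for later permitted starts the draw window closes before SVR-12 is due

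*Combined protocol and SAP*

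**What the plan says.** Several places count from the end of treatment. Section 9.1.1 defines SVR-12 as undetectable HCV RNA 12 weeks after the last Zepatier dose. The synopsis says the same under study observations and under data analysis. Notes in 8.1.3.8 and 8.1.3.9 repeat it: "SVR 12: This should occur ~12 weeks after the subject has completed treatment". Those notes ask staff to follow the post-treatment time points only as far as they can.

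The schedule counts from transplant. In the 8.2.1 table the SVR 12 row is week 24, day 168 ± 14. Section 8.1.3.9 says "Visit #10 should occur 24 weeks (171 ±7 days) after" transplantation. The table also marks day 3 ± 1 as "1 (Begin treatment") and day 91 ± 7 as "13 (End treatment").

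The start of treatment is not fixed. Section 8.1.3.3 has subjects "begin treatment once HCV RNA is confirmed, which may occur any time between weeks 1-4", and 7.1.1 says treatment begins within 4 weeks of transplant. Section 8.1.3.7 adjusts drug resupply "depending on when the subject began treatment". No such adjustment is made to the SVR-12 visit window. The one general shift, in 8.1.3.3.1, adds 4 weeks for 16-week courses.

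**The concern.** The schedule appears to be built around one early start day, while the protocol permits starts across four weeks. For a subject who starts late in that period, staff cannot both sample within the Visit 10 window and sample 12 weeks after the last dose. They must choose, and the protocol does not say which instruction prevails.

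What is at stake is the primary endpoint. A subject sampled only within the window may have a value taken too early to meet the 9.1.1 definition, or no usable value. It is also unclear how such a subject would be analysed. The synopsis divides by all subjects treated, section 10.4 describes a completers-only analysis of the primary endpoint with imputation as sensitivity, and section 10.5 calls all primary analyses intent-to-treat.

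**Working it through.** **Inputs.** Start day S: any time in weeks 1-4, so up to day 28 (7.1.1, 8.1.3.3). Course: 12 weeks = 84 days (7.1). SVR-12: 84 days after the last dose (9.1.1). Table window: 168 ± 14 = days 154-182 (8.2.1). Text window: 171 ± 7 = days 164-178 (8.1.3.9).

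**Reproducing the plan's visit days.** With S = 3: 3 + 84 = 87, 3 + 112 = 115 and 3 + 168 = 171. These are exactly the days of Visits 8 and 9 ("day 87 + 7, day 115 + 14") and Visit 10, so the visit text matches a day-3 start. The table's end-of-treatment row covers days 84-98, which fits starts on days 0-14 (84 - 84 to 98 - 84). Its centre, day 91, is 168 - 91 = 77 days, or 11 weeks, before the centre of the SVR 12 row.

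**Due date.** SVR-12 is due on S + 83 + 84 = S + 167 if once-daily dosing ends on day S + 83, or on S + 84 + 84 = S + 168 if the end of treatment is taken as S + 84. Weeks post-treatment on day 182 are (182 - (S + 84))/7 = (98 - S)/7; the S + 83 count adds one day.

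| Start day S | Due day (S+167 / S+168) | In text window, to 178 | In table window, to 182 | Weeks post-treatment on day 182 (S+84 count) |
|---|---|---|---|---|
| 3 | 170 / 171 | yes | yes | 13.6 |
| 10 | 177 / 178 | yes | yes | 12.6 |
| 11 | 178 / 179 | yes / no | yes | 12.4 |
| 12 | 179 / 180 | no | yes | 12.3 |
| 15 | 182 / 183 | no | yes / no | 11.9 |
| 16 | 183 / 184 | no | no | 11.7 |
| 21 | 188 / 189 | no | no | 11.0 |
| 22 | 189 / 190 | no | no | 10.9 |
| 28 | 195 / 196 | no | no | 10.0 |

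A sample on the nominal day 168 would be earlier still: (168 - 99)/7 = 9.9 weeks for S = 15 and (168 - 112)/7 = 8.0 weeks for S = 28.

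**Next scheduled HCV RNA.** The table ticks HCV RNA at week 24 and next at week 36 (days 245-259). Counted from S + 84, week 36 is (245 - 99)/7 = 20.9 to (259 - 99)/7 = 22.9 weeks for S = 15, and (245 - 112)/7 = 19.0 to (259 - 112)/7 = 21.0 weeks for S = 28. Weeks 28 and 32 are existing lab-only draws with viral kinetics ticked but not HCV RNA. The volume table in 8.2.2 ("Maximum Post-Transplant Blood Draw Totals") agrees: 6 mL of HCV RNA at weeks 24 and 36, 0 mL at week 28, and 84 mL in total, which is 84/6 = 14 draws. It has no week-32 row.

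**16-week courses.** The due date is S + 84 + 28 + 84 = S + 196, so days 211-224 for S = 15-28. The windows shifted by 28 days end on day 206 (text) and day 210 (table), so the same gap remains.

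**Weight of one value.** With 10 treated subjects, one value is 1/10 = 10 percentage points. If the other nine succeed, the result is 9/9 (exact 95% CI 66.4-100%) if the subject is excluded, 9/10 (55.5-99.7%) if counted as a failure, or 10/10 (69.2-100%) if counted as a success.

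**The case against.** The strongest reply is that the plan already has the right anchor. The synopsis, 9.1.1 and the notes under Visits 8-10 all count from the end of treatment, and 8.1.3.2 has staff contact subjects to coordinate research draws with routine ones. A careful team could take the sample at the right time. That stands, so a reader who inferred that the plan ties SVR-12 rigidly to transplant would go too far. But the notes are qualified, sit inside visits of which the last closes on day 178, state no tolerance, and have no ticked draw behind them for late starters.

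Other points also limit the finding:

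- The approximate 12 weeks in the notes has no stated tolerance. If about 11 weeks were acceptable, the table window would still serve starts up to about day 21 or 22.
- HCV RNA is drawn on days 3, 7, 10 and 14, so many subjects may start early.
- An empty cell is not proof that no draw is planned. Sections 8.1.3.6 and 9.2.3 require a week-28 HCV RNA test for subjects who cleared HCV or were not infected, yet neither table shows it. The footnote to the week-28 row's dagger is damaged in the text available, so a rule there cannot be excluded.
- The viral-kinetics sample includes HCV RNA (12.4.4). It is optional and depends on an agreement still to be reached, so it is only a partial backup.

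A reader might infer that an affected subject must drop out of the primary analysis. The documents do not settle that: completers is undefined, and the treated-subject denominator and the intent-to-treat statement point the other way. A reader might also infer that relapses would be missed and SVR overstated. The documents give neither the share of late starters nor the timing of relapse, and HCV RNA at weeks 36 and 52 could show a relapse later. No probability can be attached to it.

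**Conclusion.** The point holds as an unreconciled conflict within the protocol. The endpoint definition and the timing notes count from the end of treatment; the SVR 12 row and the Visit 10 window count from transplant. If the windows are followed as written, the primary endpoint is sampled before it is due for 12-week courses started from about day 11-12 (text window) or day 15-16 (table window). Each boundary moves by one day with the counting convention. The shortfall at the end of the table window is at most about one week for starts on days 15-21, and about one to two weeks for starts on days 22-28.

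The consequence is a risk of an off-time or missing primary value, not a demonstrated bias. Its frequency depends on how many subjects start late, which is not given. The conclusion rests on uninterrupted courses of the stated length, on the tables as they can be read, and on the week-28 footnote containing no additional HCV RNA rule.

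**What to change.** In the 8.2.1 table and in 8.1.3.8-8.1.3.9:

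1. Anchor the SVR-12 HCV RNA draw to the recorded date of the last first-line dose, and reconcile the two week-24 windows.
2. State an SVR-12 analysis window around 12 weeks post-treatment, with limits chosen by the team.
3. For any subject whose SVR-12 due date falls after the week-24 window closes, tick HCV RNA at the existing week-28 lab draw, or at week 32 for a 16-week course.

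Counted from S + 84, the week-28 draw (days 189-203) is (189 - 99)/7 = 12.9 to (203 - 99)/7 = 14.9 weeks post-treatment for S = 15, and (189 - 112)/7 = 11.0 to (203 - 112)/7 = 13.0 weeks for S = 28. The week-32 draw (days 217-231) gives the same values for 16-week courses. If the narrower text window is kept, the earliest affected start (S = 11) would be (189 - 95)/7 = 13.4 to (203 - 95)/7 = 15.4 weeks post-treatment at week 28. The team should weigh this when setting the limits.

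The cost is a schedule amendment and one 6 mL tube per affected subject, at a lab draw that already takes place. The week-28 footnote should be checked at the same time.
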